12.5.3 Pharmacokinetics

Individual LNP023 plasma/urine concentration data will be listed by treatment, subject, and visit/sampling time point, and plotted over time by subject.

Commercially Confidential Information

Summary statistics will include mean (arithmetic and geometric), SD, CV (arithmetic and geometric), median, minimum and maximum.

Commercially Confidential Information A geometric mean will not be reported if the dataset includes zero values.

All individual plasma concentration-time profiles for LNP023 concentration with median will be displayed graphically by treatment on semi-log view. In addition, the mean (+/- SD) and

geometric mean plasma concentration-time profiles for LNP023 by treatment over time will be displayed graphically on the linear and semi-log view.

Pharmacokinetic parameters will be calculated as described in Section 8.5.2 and will be listed by treatment and subject.

Descriptive summary statistics will include mean (arithmetic and geometric), SD, and CV (arithmetic and geometric), median, minimum and maximum. An exception to this is Tmax where median, minimum and maximum will be presented.

12.5.4 Biomarkers

All biomarker data (except for hypothesis-free platforms) will be listed by treatment, subject, and time. Summary statistics will be provided by treatment and time.

Commercially Confidential Information

Graphical measures will be used to explore relationships between LNP023 treatment and biomarkers.

Additionally graphical measures will be used to assess the relationships between changes in proteinuria and biomarker over time.

12.5.5 PK/PD relationships

Efficacy biomarkers analysed during this study will be plotted against individual PK parameters such as Cmax or AUC as well as against administered dose to establish the exposure/ response relationship and to determine the (lowest) efficacious dose or exposure.

12.6 Analysis of exploratory endpoints

12.7 Interim analyses

12.8 Sample size calculation

12.8.1 Primary endpoint(s)

Cohort A - Primary Endpoint: Reduction from baseline in log transformed UPCR.

Commercially Confidential Information

a sample size of 15 subjects provides 93% power that the primary analysis will be statistically significant at the one-sided 10% significance level assuming 20% of losses to follow-up.

Cohort B - Primary Endpoint: Change from baseline in C3 Deposit Score (based on immunofluorescence microscopy).

Commercially Confidential Information

a sample size of 12 subjects provides 94% ly significant at the one-sided 10% significance

power that the primary analysis will be statistically significant at the one-sided 10% significance level assuming 17% of losses to follow-up.

13 Ethical considerations and administrative procedures

13.1 Regulatory and ethical compliance

This clinical study was designed and shall be implemented, executed and reported in accordance with the ICH Harmonized Tripartite Guidelines for Good Clinical Practice, with applicable local regulations (including European Directive 2001/20/EC, US CFR 21), and with the ethical principles laid down in the Declaration of Helsinki.

13.2 Responsibilities of the investigator and IRB/IEC

Before initiating a trial, the investigator/institution must obtain approval/favorable opinion from the Institutional Review Board/Independent Ethics Committee (IRB/IEC) for the trial protocol, written informed consent form, consent form updates, subject recruitment procedures (e.g., advertisements) and any other written information to be provided to subjects. Prior to study start, the Investigator is required to sign a protocol signature page confirming his/her agreement to conduct the study in accordance with these documents and all of the instructions and procedures found in this protocol and to give access to all relevant data and records to Sponsor monitors, auditors, Sponsor Quality Assurance representatives, designated agents of Sponsor, IRBs/IECs, and regulatory authorities as required. If an inspection of the clinical site is requested by a regulatory authority, the Investigator must inform Sponsor immediately that this request has been made.

13.3 Publication of study protocol and results

The protocol will be registered in a publicly accessible database such as clinicaltrials.gov and as required in EudraCT. In addition, after study completion (defined as last patient last visit) and finalization of the study report the results of this trial will be submitted for publication and posted in a publicly accessible database of clinical trial results, such as the Novartis clinical trial results website and all required Health Authority websites (e.g. Clinicaltrials.gov, EudraCT etc.).

For details on the Sponsor publication policy including authorship criteria, please refer to the Sponsor publication policy training materials that were provided to you at the trial investigator meetings

13.4 Quality Control and Quality Assurance

Sponsor maintains a robust Quality Management System (QMS) that includes all activities involved in quality assurance and quality control, to ensure compliance with written Standard Operating Procedures as well as applicable global/local GCP regulations and ICH Guidelines.

Audits of investigator sites, vendors, and Sponsor systems are performed by auditors, independent from those involved in conducting, monitoring or performing quality control of the clinical trial. The clinical audit process uses a knowledge/risk based approach.

Audits are conducted to assess GCP compliance with global and local regulatory requirements, protocols and internal SOPs, and are performed according to written Sponsor processes.

14 Protocol adherence

This protocol defines the study objectives, the study procedures and the data to be collected on study participants. Additional assessments required to ensure safety of subjects should be administered as deemed necessary on a case by case basis. Under no circumstances including incidental collection is an investigator allowed to collect additional data or conduct any additional procedures for any purpose involving any investigational drugs under the protocol, other than the purpose of the study. If despite this interdiction prohibition, data, information, observation would be incidentally collected, the investigator shall immediately disclose it to Novartis and not use it for any purpose other than the study, except for the appropriate monitoring on study participants.

Investigators ascertain they will apply due diligence to avoid protocol deviations. If an investigator feels a protocol deviation would improve the conduct of the study this must be considered a protocol amendment, and unless such an amendment is agreed upon by Sponsor and approved by the IRB/IEC and health authorities, where required, it cannot be implemented.

## Commercially Confidential Information

## List of figures

## 1 Introduction

#### 1.1 Scope of document

The Review and Analysis Plan (RAP) documents contain detailed information to aid the production of Statistics & Programming input into the Clinical Study Report (CSR) for trial *"CLNP023X2202"*.

The Statistical Analysis Plan (SAP) describes the implementation of the statistical analysis planned in the protocol.

#### **1.2 Study reference documentation**

Study protocol (v03) is available at the time of finalization of the SAP.

#### 1.3 Study objectives

#### 1.3.1. Primary objective(s)

Primary objective(s)	Endpoint(s) related to primary objective(s)	
• Cohort A: To evaluate the efficacy of LNP023 in reducing proteinuria at Week 12	• Ratio to baseline of Urine Protein to Creatinine concentration Ratio (UPCR) derived from 24h urine collection.	
• Cohort B: To assess histopathological changes in kidney biopsies at Week 12	
 
Change from baseline in C3 Deposit Score (based on immunofluorescence microscopy).
 
	

#### 1.3.2. Secondary objective(s)

Secondary objective(s)	Endpoint(s) related to secondary objective(s)	
• All Cohorts: To assess the relationship between LNP023 dose and pharmacodynamic biomarkers	Biomarker levels of blood Bb	
• All Cohorts: To assess the relationship between LNP023 dose and proteinuria	• 24h urine UPCR and UACR.	
All Cohorts: To assess the effect of LNP023 on renal function	
 
(i) change in and (ii) evolution of: urinary albumin (UA), urinary protein (UP) excretion; urine albumin to creatinine ratio (UACR) urine protein to creatinine ratio (UPCR), serum creatinine, estimated glomerular filtration rate (eGFR, using
 
	

	CKD-EPI formula), creatinine clearance, hematuria
• All Cohorts: To assess the effect of LNP023 on alternative complement pathway hyperactivity	• Blood level of C3.
• All Cohorts: To assess the safety and tolerability of LNP023	• ECG parameters, vital signs, safety laboratory assessments Commercially Confidential Information, AEs and SAEs.
• All Cohorts: To assess the plasma and urine pharmacokinetics of LNP023 in patients with C3G	
 
Plasma: Non-compartmental parameter analysis related to total drug, including but not limited to Cmax, Tmax, AUClast, AUCtau and Ctrough (Cmin) after the first dose on Day 7, Day 14, Day 21 and Day 28, as well as Cmin on Days 92 and 99 or 176 and 183.
 
Urine: Non-compartmental parameters, including but not limited to total cumulative urinary excretion (Ue) and renal plasma clearance (CLr).
 

• Cohort B: To evaluate the efficacy	• Ratio to baseline of UPCR and
of LNP023 in reducing proteinuria	UACR derived from 24h urine
at Week 12	collection.

## 1.3.1. Exploratory objective(s)

#### 1.4 Study design and treatment

The study is a non-confirmatory, open-label, two cohort single arm, non-randomized study evaluating the efficacy, safety, tolerability, pharmacokinetics, pharmacodynamics and dose/biomarker relation of LNP023 in two subject populations:

- Cohort A: enrolls non-transplanted C3G subjects with reduced C3 serum levels Commercially Confidential Information
- Cohort B: enrolls subjects who have undergone kidney transplantation and have C3G recurrence.

Cohort B will start in parallel to Cohort A.

#### Commercially Confidential Information

In general, the subjects who will be enrolled into Cohort A and Cohort B, will be treated for up to 14 weeks Commercially Confidential Information with LNP023 as per the following doses and weeks:

Commercially Confidential Information

Subjects will be offered the possibility to continue LNP023 treatment for a long period by enrolling in an extension study. In this case subjects may roll-over directly into the extension study at the end of treatment period without study drug administration interruption.

#### Cohort A

Approximately 15 C3G subjects with native kidneys and with reduced serum C3 levels (male or female) will be enrolled in Cohort A to ensure that at least 12 subjects complete the study in this cohort.

Figure 1-1depicts the study design of Cohort A, which consists of a screening period that lastsup to 60 days (made up by a screening visit and a run-in period), a baseline period of about 30days (made up by two visits), a 12-week treatment periodCCI, asafety follow-up periodCommercially Confidential Information12 weeks of safety followup), and the end-of-study (EOS) visit scheduled on Day 175.

Commercially Confidential Information

Follow-up period: Commercially Confidential Information 12 weeks of safety followup without treatment. At the end of Treatment period CCI, if the Investigator does not deem it to be clinically beneficial for the subject to continue treatment, or if a subject does not want to continue treatment, the subject will enter the follow-up period.

Commercially Confidential Information

• A safety follow-up period of 12 weeks, without treatment, will follow. There will be 3 outpatient visits on Days 113, 127 and 155 Commercially Confidential Information

An end-of-study (EOS) visit is scheduled on Day 183Commercially Confidential Information

Efficacy in terms of proteinuria and individual clinical response to various pharmacodynamic markers as well as pharmacokinetics will be assessed over the 12-week treatment period.

In this context, proteinuria will be assessed by collecting 24-h urine and first morning void urine to assess the change in and evolution of: UA and UP excretion, UACR and UPCR, creatinine clearance and hematuria.

Commercially Confidential Information

**Cohort B** 

Approximately 12 C3G kidney transplanted subjects (male or female) with C3G recurrence subjects will be enrolled in Cohort B to ensure that at least 10 subjects complete the study in this Cohort.

Figure 1-3 depicts the study design of Cohort B, which consists of a screening period that lasts up to 60 days (made up by a screening visit and a run-in period), a baseline period of about 30 days (made up by two visits), a 12-week treatment period CCI , a safety follow-up period (Commercially Confidential Information 12 weeks of safety follow up) and the end-of-study (EOS) visit scheduled on Day 175.

Commercially Confidential Information

Follow-up period: A two-week down-taper of study medication and 12 weeks of safety followup without treatment. At the end of Treatment period 1 or 2, if the Investigator does not deem it to be clinically beneficial for the subject to continue treatment, or if a subject does not want to continue treatment, the subject will enter the follow-up period (refer to Figure 1-2).

Commercially Confidential Information

• A safety follow-up period up to 12 weeks with 3 outpatient visits on Days 113, 127 and 155 Commercially Confidential Information

An end of study visit scheduled on Day183 Commercially Confidential Information

Efficacy in terms of reversal of renal histopathologic changes will be assessed after the 12-week treatment period. Proteinuria and individual clinical response to various pharmacodynamic markers as well as pharmacokinetics will be assessed over the 12-week treatment period.

In this context, proteinuria will be assessed by collecting 24-h urine and first morning void urine to assess the change in and evolution of: UA and UP excretion, UACR and UPCR, creatinine clearance and hematuria.

Commercially Confidential Information

## 2 First interpretable results (FIR)

## 3 Interim analyses

Commercially Confidential Information

## 4 Statistical methods: Analysis sets

For all analysis sets, subjects will be analyzed according to the study treatment(s) received for Cohort A and B.

The safety analysis set will include all subjects that received any study drug.

The PK analysis set will include all subjects with available PK data and no protocol deviations with relevant impact on PK data.

The PD analysis set 1 will include all subjects with available PD data and no protocol deviations with relevant impact on PD data, as well as no serious adverse event

The PD analysis set 2 will include all subjects with available PD data and no protocol deviations with relevant impact on PD data.

Table 4-1	Protocol deviation codes and analysis sets	
Category Deviation c	Text description of deviation ode	Data exclusion
Subjects are	excluded from PK analysis in case of these PDs:	Exclude subject from PK analysis set
Subjects are	excluded from PD analysis in case of these PDs:	Exclude subject from PD 1 and PD2 analysis sets
COMD02	Prohibited concomitant medication-4	Yes
Subjects are PDs:	excluded from PK and PD analysis in case of these	Exclude subject from PK and PD analysis sets

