9.1.4 Study stopping rules

Novartis will review emergent safety reports on an ongoing basis to react as soon as there is a possibility that a stopping rule could apply. The Sponsor will review all SAE as individual cases and will also be able to review summaries of non-serious adverse events for patterns and trends, and will first exclude any events determined to be clearly not related to LNP023 (e.g., SAE which occurred during the pre-treatment screening period, or disease-related SAE expected in the population under study).

Enrollment in the study and dosing of affected patient(s) with LNP023 will be paused if any of the following occurs during the study:

- One fatal or life-threatening SAE that is considered by the Investigator as potentially related to LNP023
- OR two or more SAEs that are considered by the Investigator as potentially related to LNP023.

The study may resume following the safety review, if the Investigator and Sponsor agree it is safe to proceed. Restart of this clinical trial in such case will be documented by a substantial amendment and following approval by relevant health authorities.

The Sponsor could decide to stop the enrollment for early success in Cohort A in case 50% will have normal C3 blood levels (\geq 900 mg/L) at Week 12.

Page 97

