10.1.3 SAE reporting

To ensure subject safety, every SAE, regardless of causality, occurring after the subject has provided informed consent and until 30 days after the last study visit must be reported to Sponsor safety within 24 hours of learning of its occurrence. Detailed instructions regarding the submission process and requirements are to be found in the investigator folder provided to each site.

Consider the following 3 categories (as applicable) to determine SAE reporting timeframes:

- 1. Screen Failures: SAEs occurring after the subject has provided informed consent until the time the subject is deemed a Screen Failure must be reported to Sponsor.
- 2. Run-in Failures: SAEs collected between time subject signs ICF until time that subject is determined to be a run-in failure.
- 3. Treated Subjects: SAEs collected between time subject signs ICF until 30 days after the subject has discontinued or stopped study treatment (or longer, depending on the elimination half-life of LNP023).

All follow-up information for the SAE including information on complications, progression of the initial SAE and recurrent episodes must be reported as follow-up to the original episode within 24 hours of the investigator receiving the follow-up information. An SAE occurring at a different time interval or otherwise considered completely unrelated to a previously reported one must be reported separately as a new event.

If the SAE is not previously documented in the Investigator's Brochure or Package Insert (new occurrence) and is thought to be related to the study treatment, a CMO & PS Department associate may urgently require further information from the investigator for health authority reporting. The Sponsor may need to issue an Investigator Notification (IN) to inform all investigators involved in any study with the same study treatment that this SAE has been reported.

Suspected Unexpected Serious Adverse Reactions (SUSARs) will be collected and reported to the competent authorities and relevant ethics committees in accordance with EU Guidance 2011/C 172/01 or as per national regulatory requirements in participating countries.

Any SAEs experienced after the 30 day period after the last intervention or-treatment follow-up visits with no required procedures should only be reported to Sponsor Safety if the investigator suspects a causal relationship to study treatment.

10.1.4 **Pregnancy reporting**

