12.1 Analysis sets

For all analysis sets, subjects will be analyzed according to the study treatment(s) received for Cohort A and B.

The safety analysis set will include all subjects that received any study drug.

The PK analysis set will include all subjects with available PK data and no protocol deviations with relevant impact on PK data.

The PD analysis set will include all subjects with available PD data and no protocol deviations with relevant impact on PD data.

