12.4.3 Handling of missing values/censoring/discontinuations

The primary analysis will include all available data up to the point of treatment discontinuation for patients who discontinue.

Commercially Confidential Information

Subjects with missing UPRC or C3 Deposit Score values will still be included in the mixed model analysis with such data assumed missing at random (MAR).

Commercially Confidential Information

Given the severe nature of the indication and the need for close monitoring it is expected that there will be very little truly missing data.

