## 6 Statistical methods for Pharmacodynamic (PD) parameters

All subjects within the PD analysis set 1 will be included in the PD data analyses of primary and secondary objectives.

All subjects within the PD analysis set 2 will be included in the PD data analyses of exploratory objectives.

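### The SAP's primary and secondary PD analyses exclude every patient with a serious adverse event, an exclusion the protocol does not contain and that probably favours the drug

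*SAP*

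**What the plan says.** Protocol 12.1 defines a single PD population: "The PD analysis set will include all subjects with available PD data and no protocol deviations with relevant impact on PD data". On which data enter the primary analysis, protocol 12.4.3 states: "The primary analysis will include all available data up to the point of treatment discontinuation for patients who discontinue".

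SAP section 4 replaces the single set with two:

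- **Set 1** requires available PD data and "no protocol deviations with relevant impact on PD data, as well as no serious adverse event".
- **Set 2** repeats the protocol's definition: "The PD analysis set 2 will include all subjects with available PD data and no protocol deviations with relevant impact on PD data".

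The SAE clause is the only visible difference between them. SAP section 6 then assigns them: "All subjects within the PD analysis set 1 will be included in the PD data analyses of primary and secondary objectives", and "All subjects within the PD analysis set 2 will be included in the PD data analyses of exploratory objectives".

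SAP 1.1 presents the SAP as the implementation of the protocol's planned analysis, and SAP 1.2 names protocol v03 as its reference. No visible text explains the SAE clause. The sensitivity-analysis sections (SAP 6.1.3.3 and 6.2.3.1) are redacted.

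**The concern.** The population the protocol wrote for the primary analysis has been moved to the exploratory objectives, and a narrower one has taken its place. The narrowing depends on something that happens after baseline and may be related to outcome.

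- **SAEs can reflect the disease.** Protocol 9.1.4 mentions "disease-related SAE expected in the population under study". Under protocol 10.1.2, hospitalisation for the studied indication escapes SAE status only when the condition has not deteriorated, so hospitalisation for worsening C3G is an SAE.
- **There is no comparator.** Each cohort is a single arm judged on change from baseline. If the removed patients do worse, the whole shift goes into the estimated drug effect.
- **The whole patient is removed.** The Cohort A model uses Day 28/29 and Day 84/85 (SAP 6.1.3). Set 1 discards both visits, including values obtained before the event. For Covid-19 interruptions, SAP 6.2.3 ignores only the assessments after treatment stopped.
- **No time window is visible.** Protocol 10.1.3 requires reporting of "every SAE, regardless of causality, occurring after the subject has provided informed consent and until 30 days after the last study visit". If set 1 uses the SAEs so collected, an event after Week 12 could delete a valid Week 12 UPCR or biopsy score.

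At stake are the primary estimate, its 80% confidence interval and p-value in Cohort A, and the signed-rank result in Cohort B. Protocol 4.1 intends the study's data to support dose selection for confirmatory trials.

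**Working it through.** **1. The sets side by side**

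| Set | Relevant protocol deviations | SAE condition | Used for |
|---|---|---|---|
| Protocol PD set (12.1) | excluded | none | single PD set |
| SAP set 1 | excluded | SAE patients out | primary, secondary |
| SAP set 2 | excluded | none | exploratory |

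**2. The plan's own figures**

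Protocol 12.8.1 gives 93% power for 15 patients with 20% losses (Cohort A) and 94% for 12 patients with 17% losses (Cohort B), one-sided 10%. The losses reproduce: 15 × 0.80 = 12 and 12 × 0.83 = 9.96, about 10. The effect and SD are redacted, so the power itself cannot be reproduced. I solved for the standardised effect d that gives the stated power, using a one-sample t-test (an approximation to the MMRM in Cohort A and the signed-rank test in Cohort B):

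power = 1 − F(t₀.₉₀,ₙ₋₁; n−1, d√n), where F is the noncentral t distribution.

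- Cohort A: d = 0.828 at n = 12. Power is 0.911 at n = 11 and 0.887 at n = 10.
- Cohort B: d = 0.942 at n = 10. Power is 0.918 at n = 9 and 0.888 at n = 8.

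Stated power is therefore kept while total losses stay within 3 of 15 and 2 of 12. Two further losses give about 89% in each cohort. If SAE exclusions were the only losses, the binomial chance of exceeding the allowance at assumed SAE rates of 10%, 20% and 25% is:

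- More than 3 of 15: 6%, 35%, 54%.
- More than 2 of 12: 11%, 44%, 61%.

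**3. Bias under no true overall change**

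The SAE rate p and the outcome difference δ (in SD units, positive meaning SAE patients do worse) are assumptions, because the documents give neither. Each patient's change is normal with SD 1. The mean is (1−p)δ for SAE patients and −pδ for the others, so the overall mean is p(1−p)δ − (1−p)pδ = 0. Dropping SAE patients leaves a mean of −pδ. At p = 0.20 and δ = 1, that is a spurious benefit of 0.20 SD.

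False-positive rate of a one-sided 10% t-test after the exclusion, if every SAE patient has a Week 12 value (400,000 simulated trials per cell):

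| δ | n = 12: p = 10% / 20% / 25% | n = 10: p = 10% / 20% / 25% |
|---|---|---|
| −0.5 (better) | 8% / 6% / 5% | 8% / 6% / 6% |
| 0 | 10% / 10% / 10% | 10% / 10% / 10% |
| 0.5 (worse) | 13% / 16% / 18% | 13% / 15% / 17% |
| 1.0 (worse) | 17% / 24% / 28% | 16% / 23% / 26% |

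With nobody excluded the rate is about 10% throughout. The exact signed-rank test at n = 10 with untied scores and δ = 1 gives 15% / 20% / 23%, against about 10% with nobody excluded.

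**4. Allowing for patients who would be missing anyway**

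Suppose half of the SAE patients lack a Week 12 value under the protocol's rule too. At n = 12 and δ = 1, the protocol's rule itself then gives 13% / 16% / 17%. Against 17% / 24% / 28% with set 1, the clause adds about 4, 8 and 11 points. At δ = 0.5 it adds about 1.5, 3.5 and 4.5 points.

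**The case against.** **The clause may be incomplete.** The sentence ends without a full stop, and text is missing elsewhere in this SAP. A limit on timing, causality or relevance to PD may have been lost. This stands as a caveat on how broad the exclusion is. Even a limited SAE clause would still depart from protocol 12.1, and the assignment of set 1 to the primary analysis is plainly stated.

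**The SAE window is a reporting rule.** Protocol 10.1.3 does not define set 1, and it also gives a shorter window for treated patients, 30 days after stopping treatment. That is fair: removal of a valid Week 12 value by a later SAE is possible on the visible wording but is stated nowhere. The shorter window also runs past Week 12.

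**Many of these patients would be missing anyway.** Protocol 9.1.1 requires discontinuation for worsening C3G and, in Cohort B, for specified graft rejection, and 12.4.3 uses data only up to discontinuation. This reduces the added bias, as step 4 shows. If 80% of SAE patients lacked a Week 12 value, the clause would add only about 2, 4 and 5 points at δ = 1, and if all did, none in this Week 12 calculation. Under the protocol's rule, though, their earlier visits would still enter the Cohort A model.

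**The direction is inferred.** No passage links SAEs to UPCR or to the C3 Deposit Score. This stands, which is why the bias is called probable and the reverse case is shown. The untied scores assumed for Cohort B are also a simplification, because a 0 to 12 score built from graded intensities will produce ties.

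**The study is non-confirmatory, and a set 2 analysis may sit in the redacted sections.** A sensitivity analysis would not change which set the primary analysis uses. The study's status lowers the consequences, but the study still states a significance level and power.

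**Conclusion.** The concern holds. The SAP's primary and secondary PD population departs from the protocol's through a whole-patient, post-baseline exclusion with no visible reason. That conclusion rests on the text alone and needs no assumption about SAE rates.

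The bias is probably toward benefit. Its size cannot be computed from the documents. At an assumed 20% SAE rate with 12 patients, the nominal 10% error becomes about 16% to 24% if SAE patients do 0.5 to 1 SD worse and all have Week 12 values. The inflation is smaller if many discontinue first, absent if their outcomes do not differ, and reversed if they do better. Stated power suffers only when total losses exceed 3 of 15 or 2 of 12.

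This should be corrected before analysis, because it determines who is in the primary analysis of very small cohorts.

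**What to change.** In SAP section 6, assign PD analysis set 2, which is the protocol's PD set, to the primary and secondary objectives of both cohorts. Keep set 1 only as a labelled sensitivity analysis. If set 1 is kept, complete its SAE clause in SAP section 4 by stating any time window and any causality or relevance limit, with the reason.

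The cost is one line of SAP wording and a population flag. No additional data are needed, because set 2 is already defined. The estimate may become slightly less favourable.
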